10 STATISTICAL ANALYSIS PLAN

We will use descriptive statistics to describe the demographics and clinical characteristics of the study population. Means (with standard deviations) or medians (with inter-quartile ranges) will be used to summarise continuous variables, depending on their distribution and proportions to summarise categorical variables.

Total recruitment, recruitment rate, study drop-out rate and intervention adherence rate will be reported by simple descriptive statistics, or proportions where appropriate.

Semi-structured interviews will be analysed using Framework Analysis¹⁹, which will involve a five-step process:

1. Familiarisation with the data
2. Identifying a thematic framework
3. Indexing
4. Charting
5. Mapping and interpretation

The analysis will be predominantly deductive, as it will specifically focus on facilitators and barriers to study retention, and to the uptake and experience of the exercise intervention.

11 END OF TRIAL

Trial recruitment will terminate either 12 months after opening or after 40 patients have been recruited, whichever is soonest. Trial participation will cease once the final patient has completed their 26-week follow-up.

12 SAFETY REPORTING

All Adverse Events will be reported directly to the sponsor.

12.1 Adverse Event (AE)

An adverse event is any untoward medical occurrence that the patient experiences whilst participating in the clinical trial. This includes occurrences that are not necessarily caused by or related to the trial intervention.

12.2 Serious Adverse Event (SAE)

A serious adverse event (SAE) is defined as any of the following, whether or not considered related to the trial intervention.

- Results in Death
- Life-threatening (i.e. at the time of the event)*
- Requires inpatient hospitalisation or prolongation of existing hospitalisation**
- Results in persistent or significant disability or incapacity

- Is a congenital anomaly/birth defect
- Is considered medically significant by the Investigator***

*Life threatening means that the patient was at immediate risk of death from the event as it occurred. It does not include an event that, had it occurred in a more serious form, might have caused death.

**Requires in-patient hospitalisation should be defined as a hospital admission required for treatment of an adverse event.

***Considered medically significant by the Investigator are events that may not result in death, are not life threatening, or do not require hospitalisation, but may be considered a serious adverse experience when, based upon appropriate medical judgement, the event may jeopardise the patient and may require medical or surgical intervention to prevent one of the outcomes listed above.

12.3 SAEs Related to Study Procedures

Related SAEs will be any SAE that is reported as possibly, probably or definitely related to the prescribed exercise programme. See below for all definitions for the relationship to the protocol intervention.

Relationship	Description
Unrelated	There is no evidence of any causal relationship
Possible	There is some evidence to suggest a causal relationship (e.g. the event occurs within a reasonable time after administration of the trial intervention) However the influence of other factors may have been contributed to the event (e.g. the patient's clinical condition, other concomitant treatments)
Probable	There is evidence to suggest a causal relationship and the influence of other factors is unlikely
Definitely	There is clear evidence to suggest a causal relationship and other possible contributing factors can be ruled out

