1 STUDY SYNOPSIS

Study Title	EXercise TheRApy in Mesothelioma – A feasibility study (EXTRA-Meso feasibility study)
Study Sponsor	NHS Greater Glasgow and Clyde
Study Design	Randomised feasibility trial
Number of Patients	40
Patient Population	Patients with a diagnosis of mesothelioma
Primary Objective	To determine the feasibility of recruiting patients with mesothelioma to a randomised trial of exercise therapy, in order to inform design of a future phase 3 trial
Secondary Objectives	
 1. To determine barriers to study recruitment 2. To determine barriers to study retention 3. To determine safety and tolerability of the exercise programme intervention and study assessments
Primary Outcome Measure	Number of patients recruited
Secondary Outcome Measures	
 1. Proportion of screened patients who are ineligible 2. Reasons for study ineligibility 3. Study drop-out rate 4. Reasons for study drop-out 5. Intervention adherence rate 6. Adverse events 7. Health-related Quality of Life (HRQoL) questionnaire completion rate 8. Framework analysis from qualitative interviews
Eligibility Criteria	
Inclusion Criteria:
 
 1. Diagnosis of mesothelioma, ratified by a mesothelioma MDT 2. Performance status 0 -2 3. Clinical frailty score ≤ 5 4. Informed written consent 
Exclusion Criteria:
 
 1. Performance status ≥ 3 2. Clinical frailty score ≥ 6

	3. Unlikely to be able to participate in an exercise programme (clinician/physiotherapist judgement)
Screening and Consent	Patients with mesothelioma will be identified at mesothelioma MDTs, routine respiratory/oncology outpatient appointments, and during inpatient reviews. Those meeting all eligibility criteria will be provided with a Patient Information Sheet (PIS) and given sufficient time to consider participation.
Randomisation and Allocation	Following consent and baseline assessments, patients will be randomised using an online system (sealedenvelope.com) and allocated 1:1 using random permuted blocks to one of two groups: 
 A. Exercise Therapy B. Standard Care
End of Study	Trial participation will end when the last patient has completed their 26 week visit
Study duration	18 months

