5.2 Secondary Objectives

- To determine barriers to study recruitment
- To determine barriers to study retention
- To determine safety and tolerability of the exercise intervention and study assessments

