7 BASELINE ASSESSMENT

Having provided written or witnessed verbal informed consent to participate in the study, participants will all undergo the same baseline assessment. This will include recording of:

- Patient demographics, disease characteristics, including subtype and stage, co-morbidities and medication history (including current or prior systemic anti-cancer therapy).
- Routine blood results, including full blood count (FBC), C-reactive protein (CRP) and albumin
- Body Mass Index (BMI) and malnutrition universal screening tool (MUST) score
- Functional fitness measurements in the form of:
 - Hand grip strength
 - 6 minute walk distance (6MWD)
 - 30 second sit-to-stand (STS) test
- Patient related outcome measures (PROMs) via completion of the following questionnaires related to HRQoL, wellbeing and symptoms:
 - Euroquol quality of life survey (EQ-5D-5L)
 - 36-item short form survey (SF-36)
 - European organisation for research and treatment of cancer (EORTC) QLQ-C30
 - Hospital Anxiety and Depression Scale (HADS)
 - Short Warwick Edinburgh Mental Wellbeing Scale ((S)WEMWBS)
- Presence/absence of features of sarcopenia utilising:
 - Strength, assistance with walking, rising from a chair, climbing stairs, and falls (SARC-F) screening questionnaire

- Skeletal muscle area and visceral fat index measurements on routinely-acquired clinical CT scan within the preceding 3 months

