9 POST-RANDOMISATION

9.1 Standard Care Arm

Participants randomised to Standard Care will undergo routine clinical follow-up. Refer to schedule of assessments. Relevant clinical updates, including hospital admissions and any treatment updates (e.g. commencement or discontinuation of SACT) will be recorded at 8, 16 and 26 weeks post-randomisation. Participants will complete the questionnaires as per the above PROMs performed at their baseline assessment visit at 8, 16 and 26 weeks post-randomisation. If required, questionnaires can be posted out to patients and returned to the study team using a pre-paid addressed envelope. Study members can assist participants with completion of these questionnaires remotely if required. A study visit will be arranged at week 16 post randomisation to repeat functional fitness measurements as detailed above. Wherever possible, this study visit will be co-ordinated with the patient's routine clinic appointment. If the patient has had any follow-up CT scans performed as part of their routine clinical care during their study follow-up period, this will be reviewed to measure total skeletal muscle area and visceral fat index. If their MUST score indicates malnourishment at baseline assessment, a referral to NHS dietetic services will be made. During the follow-up period, patients will be sign-posted to local community activities and services that are available to promote long-term health improvement. It will be made clear to participants within the standard care arm that they are free to undertake exercise or increased physical activity if they wish. Any increase in exercise activity or participation in local generic community exercise programmes will be recorded at follow-up visits.

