12.4 Adverse Event Recording and Reporting

All AEs must be recorded on the patient's medical records. AEs must be recorded as they are reported during the visit. Full details of AEs including the nature of the event, start and stop dates, severity, relationship to study intervention and outcome must be recorded. AEs must be followed until resolution, or for at least 30 days after the trial intervention, whichever comes first or until toxicity has resolved to baseline or ≤ Grade 1, or until the toxicity is considered to be irreversible. Perceived

lack of efficacy is not an AE. An exacerbation of a pre-existing condition is an AE.

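### Related SAEs are defined only by the exercise programme, so an SAE caused by a fitness test at baseline or in standard care cannot be classed as related, although safety of the assessments is an objective

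*Combined protocol and SAP*

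**What the plan says.** The safety objective has two parts. Section 5.2 words it as "To determine safety and tolerability of the exercise intervention and study assessments", and the synopsis gives the same scope: "To determine safety and tolerability of the exercise programme intervention and study assessments".

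Section 12.3 carries the heading "SAEs Related to Study Procedures". Its operative sentence is narrower: "Related SAEs will be any SAE that is reported as possibly, probably or definitely related to the prescribed exercise programme". The causality grades that follow are introduced with "See below for all definitions for the relationship to the protocol intervention". Section 12.4 lists what must be documented for each adverse event, including "severity, relationship to study intervention and outcome must be recorded". Section 12.5 lists expected events for exercise therapy only.

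The physical tests are set out apart from the programme. Section 7 introduces them with "Functional fitness measurements in the form of" and names hand grip strength, the 6-minute walk and the 30-second sit-to-stand. Section 8 places randomisation after this baseline assessment. For standard care, section 9.1 says: "A study visit will be arranged at week 16 post randomisation to repeat functional fitness measurements as detailed above". Section 9.2 repeats this for the exercise arm and describes the programme separately, as three sessions a week for 12 weeks.

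**The concern.** The objective asks about two possible sources of harm, and the attribution rule recognises one. A participant in standard care who falls during the week-16 walk test and is admitted has no prescribed programme to which the event could be related. The same is true of anyone injured at baseline, because nobody has been allocated yet. In both cases the cause is a study procedure, and the rule in 12.3 leaves the event outside the related category.

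Attribution matters in this population. Section 12.2 makes hospital admission for an adverse event an SAE, and patients with mesothelioma can be expected to have admissions because of their disease. A total SAE count cannot by itself separate those from harm done by a test. A future phase 3 trial might use the same assessments, and this study is the stated place to learn whether they are safe.

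**Working it through.** The point concerns the scope of a definition, and the plan gives no figure of its own to reproduce. The check compares the sections and then counts the assessments affected.

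**Comparison of scope**

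| Place | Scope |
|---|---|
| Synopsis and 5.2, safety objective | Exercise intervention and study assessments |
| 12.3, heading | Study procedures |
| 12.3, defining sentence | Prescribed exercise programme |
| 12.3, causality grades | Protocol intervention |
| 12.4, relationship to be recorded | Study intervention |
| 12.5, expected events | Exercise therapy |

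The first two rows include the assessments. The remaining four do not, and no other section supplies a relatedness category for them.

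**Application of the rule**

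1. Baseline test, any participant: it precedes randomisation, so no programme has been prescribed. An SAE caused by the test cannot meet the definition.
2. Week-16 test, standard care: no programme is ever prescribed. Same result.
3. Week-16 test, exercise arm: the participant has had a programme, but there is only one relationship field. The form cannot show whether the programme or the test was the suspected cause.

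**Count of assessments**

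Inputs: 40 patients (synopsis and 6.3); 1:1 allocation, taken as 20 per arm; fitness tests at baseline and week 16 (9.4); everyone attends.

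- All assessments: 40 × 2 = 80.
- In people never yet prescribed the programme: 40 at baseline + 20 in standard care at week 16 = 60.
- Share: 60 / 80 = 75%.

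These are ceilings. At 20 recruited, the lower limit for green status in section 13, the counts are 20 + 10 = 30 of 40. With 40 recruited and an assumed 25% lost equally from both arms by week 16 (the rate that 6.3 assumes for the future trial), they are 40 + 15 = 55 of 40 + 30 = 70.

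The counts describe assessments, not events. The documents give no SAE rate for these tests, so no expected number of misclassified SAEs can be calculated.

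**Recording schedule**

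In 9.4 as it reads in the available text, the adverse-event row sits under the intervention arm and is marked at weeks 8 and 16. No such entry appears at baseline or under standard care, which is where the 60 assessments lie. Sections 12 and 12.1 contain no such limit.

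**The case against.** The strongest reply is that no event goes missing. Section 12.1 counts untoward occurrences whether or not the intervention caused them, 12.2 defines an SAE irrespective of relatedness, section 12 sends all adverse events to the sponsor, and 12.4 requires the nature and dates of each. A fall during a walk test would therefore be on record, and its cause could be recovered by reading the entry. This stands: the defect is in classification, not capture. A reader might infer that such events are lost, and the documents do not support that.

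A reader might also infer that the assessments would be found safe by construction. That does not follow either. The synopsis lists adverse events as the outcome measure, not related SAEs. Section 10 sets out no analysis of related SAEs, and the progression criteria in section 13 use only recruitment and adherence. Safety is nowhere said to be judged by the related count.

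A third inference, that test-caused events in the exercise arm would be wrongly charged to the programme, is conjecture. A 12-week programme starting around week 1 would usually have ended by the week-16 test, so the dates would often separate the two.

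The heading of 12.3 suggests a wider intent, so this may be a drafting slip. That does not remove the inconsistency, because sites could follow the heading or the sentence and classify the same event differently.

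Finally, the interviews with 10 to 20 participants (9.3) ask about the fitness assessments, and drop-out reasons are also collected. These bear on tolerability and burden. They do not attribute serious events.

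**Conclusion.** The inconsistency is real. The safety objective includes the study assessments, while 12.3 and 12.4 provide attribution to the exercise intervention alone. An SAE caused by a fitness test at baseline, or at week 16 in standard care, would be reported as an SAE but could not be classed as related under the stated rule. The related-SAE classification therefore cannot inform that part of the objective. An answer would depend on an unplanned reading of individual event records.

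The size is modest. At most 60 of 80 planned assessments fall outside any programme prescription, assuming 40 recruited, 20 per arm and full attendance. The number of SAEs affected is unknown and probably small. The primary outcome and the decision to proceed are untouched. The correction is worth making because it is cheap and gives a stated objective the attribution it lacks.

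**What to change.** 1. In 12.3, widen the definition so that an SAE counts as related when its link to either the exercise programme or a study assessment (6-minute walk, sit-to-stand, grip strength) is graded possible, probable or definite. The heading and the sentence then agree.
2. In 12.4, record the two relationships in separate fields, and report related AEs and SAEs by cause.
3. Reconcile the schedule in 9.4 with section 12 so that these events are recorded in both arms and from the baseline assessment. Without this, the new field may not be completed where most of the affected assessments occur.

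The cost is a sentence in 12.3, one extra field on the adverse-event form, and additional recording entries in the schedule. A few more SAEs may be classed as related. No treatment or study visit changes.

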12.4 Adverse Event Recording and Reporting

All AEs must be recorded on the patient's medical records. AEs must be recorded as they are reported during the visit. Full details of AEs including the nature of the event, start and stop dates, severity, relationship to study intervention and outcome must be recorded. AEs must be followed until resolution, or for at least 30 days after the trial intervention, whichever comes first or until toxicity has resolved to baseline or ≤ Grade 1, or until the toxicity is considered to be irreversible. Perceived

lack of efficacy is not an AE. An exacerbation of a pre-existing condition is an AE.

12.5 Expected Adverse Events

12.5.1 Exercise Therapy

Common (1 in 10 to 1/100)

- Fatigue
- Musculoskeletal injury
- Joint pain
- Muscle soreness

Rare (<1/100,000)

- Cardiac event such as heart attack or heart rhythm disorder

13 FEASIBILITY STUDY METRICS

Feasibility success metrics collected during this study on recruitment and adherence to study intervention, defined as completion of ≥ 18 exercise sessions across the 12 week programme) will determine if it is feasible to proceed to a phase 3 randomised trial and defined as:

- Green (proceed with no/minor changes to study design)
- Amber (significant changes to study design before proceeding)
- Red (do not proceed)

Status	Total Study Recruitment	Adherence to study intervention
Green	≥ 20 patients	$\geq 50\%$ patients
Amber	5 – 19 patients	10 – 49% patients
Red	< 5 patients	< 10% patients

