3 STUDY FLOWCHART

4 SUMMARY OF STUDY

4.1 Plain English Summary

Malignant pleural mesothelioma (MPM) is an aggressive, strongly associated with asbestos exposure. It most frequently affects the lining of the lung (pleura), but can also affect the other parts of the body, including the lining of the heart and abdomen. The incidence of MPM has been increasing over the last decade, despite legislative control of industrial asbestos use, due to a long latency period between initial exposure and development of the disease, and is predicted to continue to increase over the next 5 – 10 years.

Patients with MPM often experience troublesome symptoms including breathlessness, pain and fatigue. They can also experience anxiety and depression and feel like their quality of life is worse than before they were diagnosed. Sarcopaenia is a complex condition, where there is an interplay between inflammation and cancer, which ultimately results in low skeletal muscle mass.

Malnutrition and sarcopaenia is common in individuals with MPM, and is associated with worse outcomes, including in those who get chemotherapy.

Unfortunately, the average life expectancy following a diagnosis of mesothelioma is approximately 12 months. Currently, treatment in patients who are fit enough is aimed at prolonging this life expectancy, and involves drug treatment in the form of either chemotherapy or more recently immunotherapy. Whether a person with mesothelioma receive this treatment can depend on their physical fitness.

Exercise Therapy

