6.3 Sample size calculation

The current feasibility study will aim to recruit 40 patients. No formal sample size is feasible or appropriate, but this number is sufficient to allow identification of barriers to recruitment and retention (the latter informing the likely drop-out rate for the future phase 3 trial) and the duration and design of the exercise therapy intervention.

The primary objective of the future phase 3 trial will be to determine whether exercise therapy results in a clinically meaningful improvement in HRQOL at 16 weeks post-randomisation. Assuming a mean population score of 60 (SD 20) based on QoL scores previously reported in other mesothelioma studies, we currently estimate that a sample size of 84 patients in each arm is required to detect a 10-point improvement in EORTC QLQ C30 quality of life scores, with 90% power at 5% two-sided significance level. With a currently assumed 25% drop-out rate, based on the ‘Prehab4Cancer’ dropout rate in patients with NSCLC, we estimate that we would require a total sample size of 224 patients. Data from the current feasibility study will (a) provide a more robust estimate of baseline mean HRQOL score (based on the population score recorded from all patients at baseline assessment), (b) allow a more precise estimate of drop-out rate based on an optimised exercise intervention and (c) allow us to calculate the number of centres needed based on the recruitment rate achieved.

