6.5 Withdrawal of patients from the study

Patients will be withdrawn from the study if any of the following occur:

- Patient withdrawal of consent
- Clinical opinion of the doctor that the patient should withdraw

If a patient moves to another area during the trial follow-up period, efforts will be made to complete follow-up in conjunction with the new primary physician / team or general practitioner.

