9.2 Exercise Therapy (Intervention) Arm

Participants randomised to the Exercise Therapy arm will undergo an individualised assessment by either a physiotherapist or a qualified exercise professional with specialist cancer training, either in hospital or in the community. Refer to schedule of assessments. Following this initial assessment, patients will receive a personalised exercise, wellbeing and nutritional support package. The exercise programme will incorporate 3 sessions per week. One session per week will be supported by the physiotherapist or qualified exercise professional and the other 2 sessions will be independent sessions done in the participant's own home or local health club/gym if available. The total duration of the programme is 12 weeks. The exercise programme will incorporate both cardiovascular and resistance training, and will be progressive throughout the duration of the programme. The exercise programme will be tailored to take into account the participant's current level of fitness and familiarity/confidence with exercise, available equipment and injuries. Participants will be given a diary to record completion of each exercise session. If their MUST score indicates malnourishment at baseline assessment, a referral to NHS dietetic services will be made.

Relevant clinical updates, including hospital admissions and any treatment updates (e.g. commencement or discontinuation of SACT) will be recorded at 8, 16 and 26 weeks post-randomisation. Participants will complete the questionnaires as per the above PROMs performed at their baseline assessment visit at 8, 16 and 26 weeks post-randomisation. If required, questionnaires can be posted out to patients and returned to the study team using a pre-paid addressed envelope. Study members can assist participants with completion of these questionnaires remotely if required. A study visit will be arranged at week 16 post randomisation to repeat functional fitness measurements as detailed above. Wherever possible, this study visit will be co-ordinated with the patient's routine clinic appointment. If the patient has had any follow-up CT scans performed as part of their routine clinical care during their study follow-up period, this will be reviewed to measure total skeletal muscle area and visceral fat index. During the follow-up period, patients will be sign-posted to local community activities and services that are available to promote long-term health improvement.

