9.4 Schedule of Assessments

Visit	Pre-screening	Baseline	Week 1 (+/- 7 days)	Week 8 (+/- 2 wks)	Week 16 (+/- 3 wks)	Week 26 (+/- 4 wks)
Routine Clinical Activity						
Mesothelioma MDT review	X					
Outpatient clinic review		X				
Contrast CT thorax	X					X
Routine clinical follow-up				X	X	X
Study Activity						
Review eligibility criteria		X				
If eligible, introduce study and provide PIS		X				
Informed written consent		X				
Study registration		X				
Record baseline data		X				
Complete HRQoL questionnaires ¹		X				
Functional fitness assessment ²		X				
SARC-F screening questionnaire		X				
Review recent [#] CT for total skeletal muscle area and visceral fat index		X				
Record BMI + MUST score		X				
Randomisation		X				
Remote qualitative Interview (optional)					X	X*
Post-randomisation standard of care arm						
Record relevant clinical and/or physical activity updates				X	X	X
Complete HRQoL/wellbeing questionnaires ¹				X	X	X
Functional fitness assessment ²					X	
Review follow-up CT for total skeletal muscle area and visceral fat index						X
Post-randomisation intervention arm						
Record relevant clinical updates				X	X	X
Physiotherapist/exercise professional assessment			X			
Commence 12 week exercise programme			X			
Complete HRQoL/wellbeing questionnaires ¹				X	X	X
Review exercise session attendance and exercise compliance				X	X	X
Functional fitness assessment ²					X	
Review follow-up CT for total skeletal muscle area and visceral fat index						X
Record adverse events				X	X	

¹EQ-5D, SF-36, HADS, (S)WEBWMS and EORTC QLQ-C30 questionnaires, can be returned by post if no F2F routine clinical visit scheduled

²30 seconds sit-to-stand test, 6 minute walk test and hand grip strength

[#]Within preceding 3 months

*If not previously done

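### Does the missing denominator for the adherence colour in section 13 leave the Green/Amber decision open?

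*Combined protocol and SAP*

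**What the plan says.** Section 13 sets two progression metrics, total recruitment and adherence. A patient is adherent on completing at least "18 exercise sessions across the 12 week programme) will determine if it is feasible to proceed to a phase 3 randomised trial". Green is 50% of patients or more, Amber 10 to 49%, Red below 10%. The section does not say whether the percentage is of all patients randomised to exercise, those remaining, or those with session records.

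Section 10 is descriptive: "Total recruitment, recruitment rate, study drop-out rate and intervention adherence rate will be reported by simple descriptive statistics, or proportions where appropriate". It gives no analysis set or interval for these quantities.

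On session records, section 9.2 says "One session per week will be supported by the physiotherapist or qualified exercise professional and the other 2 sessions will be independent sessions", and adds "Participants will be given a diary to record completion of each exercise session". The schedule in section 9.4 has a line for the intervention arm at weeks 8, 16 and 26: "Review exercise session attendance and exercise compliance".

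The documents expect some patients to leave. Section 6.5 lists grounds for withdrawal ("Patients will be withdrawn from the study if any of the following occur"). Section 4.1 says that "the average life expectancy following a diagnosis of mesothelioma is approximately 12 months". Section 6.3 plans the future phase 3 trial "With a currently assumed 25% drop-out rate".

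**The concern.** The adherence colour feeds a real decision: Green means going ahead with little or no redesign, Amber means significant redesign first. If the denominator can be picked after the data are seen, the colour could be picked with it. The arm is small, about 20 patients at full recruitment, so moving a few people in or out of the denominator can cross the 50% line. Leavers are likely in this disease.

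Session counts also depend partly on patients' own records, since the supported sessions alone cannot reach 18, and no rule is given for a session without a record. With so few patients, a bare percentage may also look firmer than it is.

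**Working it through.** **Inputs.** Target 40 patients (section 6.3), randomised 1:1 (section 6): 40/2 = 20 to exercise. Three sessions a week for 12 weeks, one of them supported (section 9.2). Green at 50% or more (section 13). Drop-out of 25% is the section 6.3 assumption for phase 3, borrowed here for illustration: 20 × 0.75 = 15 remaining. True adherence, and adherence among drop-outs, are my assumptions. Section 13 gives no derivation of its cut-offs, so there is no plan figure to reproduce.

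**Sessions.** 3 × 12 = 36 planned and 1 × 12 = 12 supported, so 18 requires at least 18 − 12 = 6 independent sessions. At full pace 18 is reached in 18/3 = 6 weeks, so someone who leaves later may already be adherent.

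**Which counts change colour.** Take 20 against 15, with all five leavers non-adherent:

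| Adherent | Of 20 | Of 15 |
|---|---|---|
| 7 | 35% Amber | 47% Amber |
| 8 | 40% Amber | 53% Green |
| 9 | 45% Amber | 60% Green |
| 10 | 50% Green | 67% Green |

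Every other count from 0 to 15 keeps its colour, and none moves into or out of Red. The probability of exactly 8 or 9 adherent out of 20 is 34%, 28% and 11% for true adherence of 40%, 50% and 60%. Other patterns can also cross the line: 9/18 = 50% if two non-adherent patients are left out. In the opposite direction, 10/20 = 50% becomes 7/15 = 47% if five leave and three of them were already adherent.

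**Chance of Green.** Over all randomised it is P(X ≥ 10), with X binomial (20, p). With drop-outs excluded, let d be the drop-out proportion and q the adherence among drop-outs. Adherence among those remaining is r = (p − dq)/(1 − d). The chance of Green is the sum over k of P(k drop-outs out of 20) × P(at least half of the 20 − k remaining are adherent, each with probability r).

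With d = 0.25:

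| True adherence p | All randomised | Excluded, q = p | Excluded, q = 0 |
|---|---|---|---|
| 30% | 5% | 7% | 26% |
| 40% | 24% | 26% | 65% |
| 50% | 59% | 55% | 93% |
| 60% | 87% | 82% | over 99% |

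For example, at p = 0.4 and q = 0, r = 0.4/0.75 = 0.533. At p = 0.4 and q = 0.2, r = (0.4 − 0.05)/0.75 = 0.467 and the chance of Green is 45%. At p = 0.4 and q = 0, it is 36%, 55% and 75% for drop-out of 10%, 20% and 30%.

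**Interval.** Exact (Clopper-Pearson) 95% limits are 23% to 68% for 9/20, 27% to 73% for 10/20, and 19% to 81% for 5/10 (the arm size at the Green recruitment floor of 20). They need only the numerator and denominator.

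**The case for a change.** The strongest case for a change is that section 13 says these metrics will decide progression, so one dataset should give one answer. The text does not forbid leaving drop-outs out. The counts that change colour lie next to the Green boundary, where the rule has to discriminate. A drop-out who never reached 18 sessions is a plausible patient here, and the 24% against 65% contrast is not small. Naming the denominator would take a sentence or two and no new data.

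The omission is real, and the arithmetic is right. What does not stand is the step from an unwritten definition to an open decision. In the section 13 table the recruitment column counts everyone recruited, and the adherence column uses the same word with no restriction to completers or evaluable patients. The narrower denominator has to be supplied by the reader. The largest shifts also need every drop-out to be non-adherent, although 18 sessions can be completed by week 6. The 25% comes from lung cancer patients and is meant for a trial with a 16-week endpoint, whereas adherence here is counted over 12 weeks. Drop-out and its reasons are reported outcomes, so a reader can see who left.

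Rules for deaths, unrecorded sessions and differing colours are also unwritten, but each has a sensible default or is a matter of judgement. Counting every death as non-adherent, for instance, would mix mortality with acceptability of the programme. Session records do not rest on the diary alone, given the weekly supported session and the scheduled reviews.

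**Conclusion.** No change to the plan is needed. The denominator is a detail left unwritten that an analyst would fill sensibly: patients with at least 18 recorded sessions over all patients randomised to exercise, with leavers kept in and classed by the sessions they completed. On that reading the colour is unique.

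On the alternative reading, the difference is near nil if drop-out is unrelated to adherence (at most 5 percentage points in the chance of Green across true adherence of 30% to 60% at 25% drop-out). It is large, 24% against 65% at 40% adherence, only if drop-outs are excluded and none was adherent. That result rests on a borrowed drop-out rate and an assumption about drop-outs that the documents do not make.

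The interval is optional reporting. It would show how little about 20 patients can establish, but it does not move the colour, and any reader can compute it from the published counts. A descriptive analysis suits a study that section 6.3 says has no formal sample size.
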